4 LIST OF ABBREVIATIONS AND DEFINITIONS OF TERMS

Abbreviation	Term
ADL	activities of daily living
AE	adverse event
ALT	alanine aminotransferase
ASCO	American Society of Clinical Oncology
AST	aspartate aminotransferase
BP	blood pressure
CA	competent authorities
CFR	Code of Federal Regulations
CI	confidence interval
CL/F	apparent clearance
CR	complete response
CRA	clinical research associate
CRF	case report form
CRO	Clinical Research Organization
CSR	clinical study report
CTC	Common Toxicity Criteria
CTCAE	Common Terminology Criteria for Adverse Events
CV	curriculum vitae
DTC	differentiated thyroid cancer
EC	European Communities
ECG	electrocardiogram
ECOG	Eastern Cooperative Oncology Group
EU	European Union
FDA	Food and Drug Administration
g-CSF	granulocyte colony-stimulating factor
GCP	Good Clinical Practice
GGT	γ-glutamyl transpeptidase
ICF	informed consent form
ICH	International Council for Harmonisation of Technical Requirements for Pharmaceuticals for Human Use

Abbreviation	Term	
IEC	Independent Ethics Committee	
IND	Investigational New Drug	
IRB	Institutional Review Board	
IVRS/IWRS	interactive voice/web response system	
LLN	lower limit of normal	
LMWH	low-molecular-weight-heparin	
LVEF	left ventricular ejection fraction	
MedDRA	Medical Dictionary for Regulatory Activities	
MHRA	Medicines and Healthcare Products Regulatory Agency	
MUGA	multigated acquisition scan	
NSAID	nonsteroidal anti-inflammatory drug	
ORR	objective response rate	
OS	overall survival	
PD	progressive disease	
PR	partial response	
PFS	progression-free survival	
PI	principal investigator	
РК	pharmacokinetic(s)	
PRT	palliative radiotherapy	
PSC	Protocol Steering Committee	
PT	preferred term	
RECIST	Response Evaluation Criteria in Solid Tumors	
RR-DTC	radioiodine-refractory differentiated thyroid cancer	
SAE	serious adverse event	
SOC	system organ class	
SOP	standard operating procedure	
SUSARs	suspected unexpected serious adverse reactions	
TEAEs	treatment-emergent adverse events	
TKI	tyrosine kinase inhibitor	
TTP	time to progression	
ULN	upper limit of normal	

Abbreviation	Term
US/USA	United States of America
VEGF	vascular endothelial growth factor
VEGFR	vascular endothelial growth factor receptor
WBC	white blood cell (count)

5 ETHICS

5.1 Institutional Review Boards/Independent Ethics Committees

The protocol, informed consent form (ICF), and appropriate related documents must be reviewed and approved by an Institutional Review Board (IRB) or Independent Ethics Committee (IEC) constituted and functioning in accordance with ICH E6 (Good Clinical Practice), Section 3, and any local regulations. Any protocol amendment or revision to the ICF will be resubmitted to the IRB/IEC for review and approval, except for changes involving only logistical or administrative aspects of the study (eg, change in CRA[s], change of telephone number[s]). Documentation of IRB/IEC compliance with the ICH E6 and any local regulations regarding constitution and review conduct will be provided to the sponsor.

A signed letter of study approval from the IRB/IEC chairman must be sent to the principal investigator with a copy to the sponsor before study start and the release of any study drug to the site by the sponsor or its designee (ICH E6, Section 4.4). If the IRB/IEC decides to suspend or terminate the study, the investigator will immediately send the notice of study suspension or termination by the IRB/IEC to the sponsor.

Study progress is to be reported to IRB/IECs annually (or as required) by the investigator or sponsor, depending on local regulatory obligations. If the investigator is required to report to the IRB/IEC, he/she will forward a copy to the sponsor at the time of each periodic report. The investigator(s) or the sponsor will submit, depending on local regulations, periodic reports and inform the IRB/IEC of any reportable adverse events (AEs) per ICH guidelines and local IRB/IEC standards of practice. Upon completion of the study, the investigator will provide the IRB/IEC with a brief report of the outcome of the study, if required.

At the end of the study, the sponsor should notify the IRB/IEC and Competent Authority (CA) within 90 days. The definition of the end of the study is the date of the data cutoff for the final analysis or last subject/last visit, including discontinuation from the study for any reason, whichever occurs later.

The sponsor should also provide the IRB/IEC with a summary of the study's outcome.

In the case of early termination/temporary halt of the study, the investigator should notify the IRB/IEC and CA within 15 calendar days, and a detailed written explanation of the reasons for the termination/halt should be given.

5.2 Ethical Conduct of the Study

This study will be conducted in accordance with standard operating procedures of the sponsor (or designee), which are designed to ensure adherence to GCP guidelines as required by the following:

• Principles of the World Medical Association Declaration of Helsinki 2014

- ICH E6 Guideline for GCP (CPMP/ICH/135/95) of the European Agency for the Evaluation of Medicinal Products, Committee for Proprietary Medicinal Products, International Council for Harmonisation of Technical Requirements for Pharmaceuticals for Human Use
- Title 21 of the United States Code of Federal Regulations (US 21 CFR) regarding clinical studies, including Part 50 and Part 56 concerning informed subject consent and IRB regulations and applicable sections of US 21 CFR Part 312
- A waiver from the IRB(s)/IEC(s) will be obtained before study initiation for non-US studies conducted under an Investigational New Drug (IND) application.
- European Good Clinical Practice Directive 2005/28/EC and Clinical Trial Directive 2001/20/EC for studies conducted within any EU country. All SUSARs will be reported, as required, to the Competent Authorities of all involved EU member states.
- Article 14, Paragraph 3, and Article 80-2 of the Pharmaceutical Affairs Law (Law No. 145, 1960) for studies conducted in Japan, in addition to Japan's GCP
- Other applicable regulatory authorities' requirements or directives

5.3 Subject Information and Informed Consent

As part of administering the informed consent document, the investigator must explain to each subject or guardian/legally authorized representative the nature of the study, its purpose, the procedures involved, the expected duration, the potential risks and benefits involved, any potential discomfort, potential alternative procedure(s) or course(s) of treatment available to the subject, and the extent of maintaining confidentiality of the subject's records. Each subject must be informed that participation in the study is voluntary, that he/she may withdraw from the study at any time, and that withdrawal of consent will not affect his/her subsequent medical treatment or relationship with the treating physician.

This informed consent should be given by means of a standard written statement, written in nontechnical language. The subject or the subject's legally acceptable representative should understand the statement before signing and dating it and will be given a copy of the signed document. If a subject is unable to read or if a legally acceptable representative is unable to read, an impartial witness should be present during the entire informed consent discussion. After the ICF and any other written information to be provided to subjects is read and explained to the subject or the subject's legally acceptable representative, and after the subject or the subject's legally acceptable representative, and after the subject or the subject's legally acceptable representative. The subject's participation in the study and, if capable of doing so, has signed and personally dated the ICF, the witness should sign and personally date the consent form. The subject will be asked to sign an ICF before any study-specific procedures are performed. No subject can enter the study before his/her informed consent has been obtained.

An unsigned copy of an IRB/IEC-approved ICF must be prepared in accordance with ICH E6, Section 4, and all applicable local regulations. Each subject must sign an approved ICF before study participation. The form must be signed and dated by the appropriate parties. The original, signed ICF for each subject will be verified by the sponsor and kept on file according to local procedures at the site.

The subject or the subject's legally authorized representative should be informed in a timely manner if new information becomes available that may be relevant to the subject's willingness to continue participation in the study. The communication of this information should be documented.

6 INVESTIGATORS AND STUDY PERSONNEL

This study will be conducted by qualified physicians under the sponsorship of Eisai (the sponsor) at an unspecified number of treatment sites.

The name and contact information of the sponsor's study team members and any Contract Research Organizations (CROs) used for this study are listed in the Physician Information Package provided to each site.

7 INTRODUCTION

Lenvatinib is an investigational tyrosine kinase inhibitor (TKI) agent and it has completed clinical registration studies for the treatment of radioiodine-refractory differentiated thyroid cancer (RR-DTC) and unresectable Hepatocellular Carcinoma. Moreover, a multicenter, open-label, randomized, Phase 3 trial is ongoing to compare the efficacy and safety of lenvatinib in combination with everolimus or pembrolizumab versus sunitinib alone in first-line treatment of subjects with advanced renal cell carcinoma (E7080-G000-307). Based on its efficacy and safety profile, lenvatinib was granted approval to treat patients with progressive, DTC whose disease progressed despite receiving radioactive iodine therapy disease (Lenvima approval for DTC,13 Feb 2015). Moreover, lenvatinib was approved for use in combination with everolimus (Afinitor[®]) in the treatment of advanced renal cell carcinoma following one prior antiangiogenic therapy (FDA Approved Drugs, 13 May 2016).

The activity of lenvatinib for treatment of patients with advanced, progressive DTC unresponsive to conventional radioiodine therapy has been initially established in a Phase 2 trial E7080-G000-201, which enrolled 58 patients with RR-DTC (Cabanillas, et al., 2015) and 59 patients with medullary thyroid cancer. The primary efficacy endpoint of this study was the objective response rate (ORR) based on the assessments by the independent imaging review using modified Response Evaluation Criteria in Solid Tumors (RECIST). In the RR-DTC cohort, the ORR was 50%; 59% in patients with prior VEGF/VEGFR-targeted treatment and 46% in patients without prior vascular endothelial growth factor (VEGF)/ vascular endothelial growth factor receptor (VEGFR)-targeted therapy. The median estimate of progression-free survival (PFS), at a minimum follow-up of 14 months, was 12.6 months. The 6-months PFS rate was 78% and the 12-months PFS rate was 55%. The overall survival

(OS) rate was 86% at 12 months and was 78% at both 18 and 24 months. The most frequently reported (>40% of all patients) treatment-emergent adverse events (TEAEs) were diarrhea, hypertension, proteinuria, fatigue, weight decreased, decreased appetite, nausea, headache, cough, and dysphonia. In the DTC cohort, the most commonly reported Grade 3 TEAEs (occurring in approximately 10% of patients) were hypertension, weight decrease, diarrhea, and proteinuria.

The efficacy and safety of lenvatinib treatment has also been evaluated in the multicenter. randomized, double-blind, placebo-controlled Phase 3 trial E7080-G000-303 (SELECT trial) in patients with RR-DTC with documented disease progression within 13 months. Patients were stratified by age (≤ 65 , > 65 years), region and ≤ 1 prior VEGFR-targeted therapies and randomized 2:1 to lenvatinib or placebo arms (24 mg a day, 28-day cycle). The primary endpoint was PFS assessed by Independent Radiologic Review; the secondary endpoints included ORR (ie, complete response [CR] + partial response [PR]), OS, and safety. A total of 392 patients (63.0 years median age; 51.0% male) were randomized at over 100 sites in Europe, North and South America, and Asia. Patients in the lenvatinib arm had a significantly prolonged PFS (hazard ratio = 0.21, 95% confidence interval [CI] = 0.14-0.31; $P \le 0001$) with a median PFS for the lenvatinib arm of 18.3 months (95% CI = 15.1-not evaluable) vs the placebo arm: 3.6 months (95% CI = 2.2–3.7). The lenvatinib arm PFS benefit was observed in all predefined subgroups: median lenvatinib arm PFS for patients with prior vs no prior VEGF-therapy was 15.1 months (n=66) and 18.7 months (n=195). respectively; rates (n) of CRs for the lenvatinib arm vs placebo arm were 1.5% (4) and 0, respectively; PRs for the lenvatinib arm vs the placebo arm were 63.2% (165) and 1.5% (2), respectively. Median exposure durations for the lenvatinib arm vs the placebo arm were 13.8 months and 3.9 months, respectively; median time to lenvatinib response was 2.0 months. Median OS has not been reached; deaths for the lenvatinib arm were 71 (27.2%) and for the placebo arm were 47 (35.9%). The 5 most common lenvatinib treatment-related adverse events (AEs) (any grade) were hypertension (68%), diarrhea (59%), appetite decreased (50%), weight loss (46%), nausea (41%). The most common Grade \geq 3 lenvatinib treatmentrelated AEs (\geq 5%) were hypertension (42%), proteinuria (10%), weight loss (10%), diarrhea (8%), and appetite decreased (5%). The lenvatinib dose was reduced in 78.5% of patients and lenvatinib was discontinued due to AEs in 14.2% of patients (Schlumberger, et al., 2014). Based on the efficacy and safety information to date, patients with RR-DTC may benefit from lenvatinib treatment.

In regards to efficacy and safety in RCC, the Phase 2 portion of Study E7080-G000-205 enrolled 153 patients with advanced or metastatic, clear- cell, RCC who had a history of receiving 1 prior VEGF agent. A total of 153 patients were randomized in a 1:1:1 ratio to receive treatment with lenvatinib plus everolimus, lenvatinib (24 mg once daily [QD]), or everolimus (10 mg QD). The safety profile for lenvatinib plus everolimus was consistent with the known toxic effects of each individual agent, with no unexpected TEAEs observed. The most common TEAEs of any grade in the lenvatinib plus everolimus arm were diarrhea and fatigue or asthenia. Grade 3 and 4 events occurred in fewer patients allocated singleagent everolimus (25 [50%]) compared with those assigned lenvatinib alone (41 [79%]) or lenvatinib plus everolimus (36 [71%]). The most common Grade 3 or 4 TEAEs in patients allocated lenvatinib plus everolimus was diarrhea (10 [20%]), in those assigned single-agent lenvatinib it was proteinuria (10 [19%]), and in those assigned single- agent everolimus it was anemia (6 [12%]). Two deaths were deemed related to study drug, 1 cerebral hemorrhage in the lenvatinib plus everolimus group and 1 myocardial infarction with single-agent lenvatinib (Motzer, et al., 2015a).

In regards to efficacy and safety in unresectable HCC, lenvatinib has been evaluated in the Phase 3 study of "A Multicenter, Randomized, Open-Label, Phase 3 Trial to Compare the Efficacy and Safety of Lenvatinib (E7080) Versus Sorafenib in First-Line Treatment of Subjects With Unresectable Hepatocellular Carcinoma" (E7080-G000-304). This was a non-inferiority study of patients who had unresectable HCC with ≥ 1 measurable target lesion, Barcelona Clinic Liver Cancer stage B or C, Child-Pugh class A, Eastern Cooperative Oncology Group (ECOG) $PS \le 1$, and with no prior systemic therapy. Among 954 enrolled patients, 478 patients received lenvatinib while 476 received sorafenib and were randomized 1:1 to lenvatinib (body weight \geq 60 kg: 12 mg/day; < 60 kg: 8 mg/day) or the comparator arm of sorafenib 400 mg twice daily. The efficacy of lenvatinib has been demonstrated to be non-inferior in terms of OS, and achieved statistically significant and clinically meaningful improvements in PFS, time to progression (TTP) and ORR by modified RECIST as first line therapy for unresectable hepatocellular carcinoma. The TEAEs were consistent with the known lenvatinib safety profile. Most common lenvatinib TEAEs were hypertension (42%), diarrhea (39%), decreased appetite (34%), decreased weight (31%), and fatigue (30%) (Cheng, et al., 2017). As there are patients who are continuing treatment from several ongoing clinical studies of different phases in the lenvatinib program at Eisai, the "roll-over" study will allow those patients to continue to receive their treatments of lenvatinib as monotherapy or in combination regimen provided that they are deriving clinical benefit. Long-term safety will be assessed in patients in this study.

8 STUDY OBJECTIVES

8.1 Primary Objective

The primary objective is to assess long-term safety of study drug(s) in subjects who are enrolled in Eisai-sponsored lenvatinib studies.

8.2 Secondary Objective(s)

Not applicable.

9 INVESTIGATIONAL PLAN

9.1 Overall Study Design and Plan

This is an open-label extension study to roll-over eligible subjects from Eisai sponsored lenvatinib studies. The subject can be enrolled in the roll-over study for the purpose of long-term safety data collection. The transition would occur after the completion and evaluation of the primary endpoint of the parent studies or after all study data for the primary outcome measure were evaluated for the parent study. The parent study is defined as the Eisai-sponsored lenvatinib clinical study in which the subject was receiving lenvatinib either as monotherapy or as combination therapy, or was receiving any other comparator therapy. The subjects willing to participate in the roll-over study have to sign the ICF for Study E7080-G000-604. The "End of Treatment" assessments in the parent study are to be completed and reviewed by the investigator prior to subject enrollment into Study E7080-G000-604. The eligibility for the roll-over study is to be established based on meeting all inclusion and exclusion criteria described in Section 9.3. The intention is that the subject will not be without study drug during transition from the parent study to the roll-over study. The subjects in Study E7080-G000-604 should receive the first dose of the study drug the following day after the last dose of the study drug in the parent study. All TEAEs and SAEs, regardless of relationship to study drug or procedure, should be recorded beginning from the time the subject signs the roll-over study ICF for up to 28 days after last dose of study drug(s) (or 5 × half-life of study drug[s], whichever is longer). SAE management and reporting requirements specific to study drugs will be addressed as per the instructions in the parent study protocol. Ongoing AEs in the parent study will remain ongoing at the time of discontinuation in the parent study, and the roll-over study will only capture new or worsening TEAEs occurring after signing the roll-over study ICF.

Figure 1 Study Design for Study E7080-G000-604

Screening period: From approximately Day -30 to Day -1, subjects may remain on the parent study.

Cohort A: Subjects who received lenvatinib monotherapy or who crossed over from a comparator arm to receive lenvatinib monotherapy in their parent study will continue to receive lenvatinib monotherapy

Cohort B: Subjects who received lenvatinib combination therapy or who crossed over from a comparator arm to receive lenvatinib combination therapy in their parent study will continue to receive lenvatinib combination therapy

Cohort C: Subjects who received comparator treatment in their parent study will continue to receive comparator treatment, with exception of subjects receiving placebo* **Discontinuation criteria**: progression of disease, unacceptable toxicity, subject request, withdrawal of consent, termination of study by sponsor, use of non-permitted concomitant drugs, unacceptable non-compliance with the protocol, subject lost to follow-up.

Subjects will be permitted to continue study drug(s) beyond initial disease progression as long as the treating investigator considers that there is continued clinical benefit after discussing with the sponsor and if the subject is tolerating the study drug(s). * Subjects who received placebo in their parent study and who were either not permitted to cross over or who opted not to cross over to active treatment will not be eligible to enroll in

this study.

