9.4 Treatment(s)

9.4.1 Treatment(s) Administered

Subjects enrolled from parent study will enter the roll-over study and will continue the study drug of lenvatinib, or combination regimen, or any other comparator therapy (except placebo) at the same doses upon discontinuation of the parent study. Study drug(s) administered will be recorded in the case report form (CRF).

Subject must not be dispensed more than a 3-months supply of study drug(s) at any particular time during participation in Study E7080-G000-604.

For China Only:

Comparator Drug: Sorafenib

The subject(s) who receive the comparator in the parent study will be enrolled to Cohort C. In the event that comparator clinical supply is limited, the comparator treatment may be obtained commercially from local sources and reimbursed by the sponsor unless this is prohibited by specific country laws. Further instructions on acquisition procedures for commercial supply will be provided by the sponsor.

Criteria for Interruption of Treatment, Dose Reduction and Resumption

Dose reduction and interruptions for subjects who experience toxicity will be made according to the guidelines provided in the parent protocol.

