9.4.1.5 Drug-Drug Interactions

Lenvatinib's weak in vitro inhibitory and induction potential on cytochrome P450 enzymes (CYP P450) (Study No. XT063020) suggests a low risk of lenvatinib interference with the PK of other drugs metabolized by CYP P450 enzymes which are co-administered in usual clinic practice. Nonclinical studies identify CYP3A4 as the important CYP isozyme responsible for human hepatic metabolism of lenvatinib. However, clinical studies conducted showed that co-administration of lenvatinib with CYP3A4/P-glycoprotein (P-gp) inhibitors or inducers is not of clinical concern. The main metabolic pathways for lenvatinib in humans were identified as enzymatic (CYP3A and aldehyde oxidase) and non-enzymatic processes (LENVIMA[®] Package Insert). Please refer to Appendix 1 and http://medicine.iupui.edu/clinpharm/ddis/ for the most current information.

For subjects receiving everolimus, drugs or substances (including herbal supplements or grapefruit juice) known to be potent inhibitors of CYP3A4/P-gp should not be used. Potent inducers of CYP3A4/P-gp should not be used unless there is no alternative treatment available. Moderate/ weak inhibitors or inducers or substrates of CYP3A4 and/or P-gp should be used with caution. Dose reduction of everolimus may be considered when coadministering moderate CYP3A4 or P-gp inhibitors. For further information please refer to the prescribing information. No formal pharmacokinetic drug interaction studies have been conducted with pembrolizumab. Pembrolizumab is a monoclonal antibody; pharmacokinetic interactions with lenvatinib (and vice-versa) are not expected. Strong CYP3A4 inhibitors such as ketoconazole may increase sunitinib plasma concentrations. CYP3A4 inducers such as rifampin may decrease sunitinib plasma concentrations. Selection of an alternate concomitant medication with no or minimal enzyme inhibition or induction is recommended. A dose reduction for sunitinib to a minimum of 37.5 mg daily should be considered if sunitinib must be co-administered with a strong CYP3A4 inhibitor. A dose increase for sunitinib to a maximum of 87.5 mg daily should be considered if sunitinib must be co-administered with a CYP3A4 inducer. If dose is increased, the patient should be monitored carefully for toxicity. In regards, to lenvatinib combination regimen, please refer to drug-drug interactions section in the parent study.

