9.7.1.6 Safety Analyses

All safety analyses will be performed on the Safety Analysis Set. All safety analyses will be summarized separately by treatment group. TEAEs and SAEs will be summarized using descriptive statistics. Time to treatment discontinuation due to a TEAE, number of dose reductions, and time to first dose reduction will be summarized.

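### Treatment group is never defined, and Cohorts B and C can each hold different drugs, so neither the SAP's region columns nor cohort columns would reliably show safety by regimen

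*Protocol*

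**What the plan says.** **Cohorts.** Protocol 9.1 (Figure 1 text), repeated in SAP 4.2, sets three cohorts. Cohort A is lenvatinib monotherapy. Cohorts B and C are broader: "Cohort B: Subjects who received lenvatinib combination therapy or who crossed over from a comparator arm to receive lenvatinib combination therapy" and "Cohort C: Subjects who received comparator treatment in their parent study will continue to receive comparator treatment", excluding placebo. Neither definition names a partner or comparator drug, and neither document defines a smaller treatment unit.

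**Drugs foreseen.** The Protocol Introduction describes an ongoing sponsor trial of "lenvatinib in combination with everolimus or pembrolizumab versus sunitinib alone in first-line treatment". Protocol 9.4.1.5 gives interaction text for everolimus, pembrolizumab and sunitinib; the everolimus text is addressed to subjects on that drug: "For subjects receiving everolimus, drugs or substances (including herbal supplements or grapefruit juice) known to be potent inhibitors of CYP3A4/P-gp should not be used". Protocol 9.4.1, in its China-only text, states "Comparator Drug: Sorafenib" and places those subjects in Cohort C.

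**Reporting unit.** Protocol 9.7.1.6: "All safety analyses will be summarized separately by treatment group". No section says whether that means cohort or regimen. SAP section 4 plans summaries for China, Rest of World and all subjects. The table list in SAP 6.5.2 contains no cohort, treatment-group or regimen split.

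**Drug-level outputs.** SAP 6.5.1 summarizes dose intensity in mg/day without saying for which drug. In SAP 6.5.2 the dosing listing covers lenvatinib, and the discontinuation table covers stopping lenvatinib.

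**Data.** Protocol 9.4.1 records the study drugs administered on the CRF, and Protocol 9.4.3 records the kit dispensed.

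**The concern.** The only objective is the long-term safety of the study drugs. The SAP's region and overall columns can combine lenvatinib alone, lenvatinib combinations and comparators. The obvious repair is to add columns for Cohorts A, B and C, but that would still leave B and C as possible mixtures of different drugs, in proportions set by whichever parent studies happened to contribute.

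An event specific to one partner or comparator would then be divided by subjects who never took that drug, and could be credited to lenvatinib combinations or comparators in general. The causality data cannot recover the difference, because Protocol 9.5.7.3 asks a single yes/no question about the study drugs taken together.

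**Working it through.** There is no sample size, power or target precision to reproduce; both documents say that none was calculated. The check is a reading of the definitions, followed by illustrative arithmetic.

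**1. Can two regimens share a cohort?** Cohort B admits any lenvatinib combination, and two partners are named in the protocol. Cohort C admits any non-placebo comparator, and sorafenib and sunitinib are both named. Pooling is therefore permitted. Neither document lists the regimens enrolled or their numbers.

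**2. Effect on an event rate.** Let *w* be the share of the cohort on the regimen with rate *p*, and *q* the rate on the other regimen. The cohort column shows *w·p + (1 − w)·q*.

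Take *p* = 20%, the size of the Grade 3 or 4 diarrhea rate that the Protocol Introduction gives for lenvatinib plus everolimus. The values of *w* and *q* are assumptions.

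| *q* | *w* = 0.25 | *w* = 0.50 | *w* = 0.75 |
|---|---|---|---|
| 0% | 5% | 10% | 15% |
| 5% | 8.8% | 12.5% | 16.3% |
| 20% | 20% | 20% | 20% |

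For example, 0.25 × 20% + 0.75 × 5% = 8.75%. At *w* = 1 the column shows 20% whatever *q* is. Dilution needs both a mixed cohort and unequal rates.

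**3. Effect on dose intensity.** The Protocol Introduction gives sorafenib as 400 mg twice daily in the hepatocellular carcinoma trial, which is 800 mg/day. Protocol 9.4.1.5 mentions sunitinib daily figures of 37.5 and 87.5 mg. These serve here only to show the difference in scale. At an assumed 50:50 mix:

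- 0.5 × 800 + 0.5 × 37.5 = 418.75 mg/day
- 0.5 × 800 + 0.5 × 87.5 = 443.75 mg/day

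Neither result describes a drug that anyone took. If SAP 6.5.1 is instead read as lenvatinib only, Cohort C exposure is not summarized at all.

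**4. Precision after splitting.** About 50 subjects were initially expected; regimen sizes are assumed. The limits are exact binomial.

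| Subjects on regimen | Observed | Exact 95% interval | One-sided 95% upper limit if no event is seen, 1 − 0.05^(1/n) | Chance of at least one event at a true 12%, 1 − 0.88^n |
|---|---|---|---|---|
| 5 | 1 (20%) | 0.5% to 71.6% | 45.1% | 47% |
| 10 | 2 (20%) | 2.5% to 55.6% | 25.9% | 72% |
| 25 | 5 (20%) | 6.8% to 40.7% | 11.3% | 96% |

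The 12% is the Grade 3 or 4 anemia rate that the Protocol Introduction gives for everolimus alone; it is used only for scale.

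**The case against.** **No cohort table is planned.** The cohorts assign continuing treatment, and neither document makes them analysis strata. On this view the real defect is the undefined treatment group, which the SAP drops. This stands, and it is why the point begins there. But the choice of definition decides whether the repair works, and the cohort is the only treatment unit that the documents offer.

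**Pooling is possible, not shown.** A reader might infer that Cohorts B and C do mix regimens. The documents do not support that: the Introduction is background, the interaction text shows only that certain drugs were anticipated, and sorafenib in China is the only comparator explicitly tied to Cohort C.

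**Some regimens would be separable.** A reader might also infer that cohort reporting would give no regimen's safety. That goes too far. Cohort A is lenvatinib alone, and a China-by-Cohort-C column would hold sorafenib, the only comparator named for China. No such column is planned, however.

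**The protocol's own contrast does not measure the problem.** The Introduction's Grade 3 and 4 rates of 50% (everolimus), 71% (lenvatinib plus everolimus) and 79% (lenvatinib) show that toxicity varies by regimen. Under the cohort definitions those three regimens would fall in different cohorts, so they say nothing about spread within B or within C.

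**The gain is limited.** The study is descriptive, regimen columns may be sparse, and all TEAEs are already listed by subject. The table shells and programming specifications are separate documents, so a regimen variable may exist there. These points favor counts over percentages in small groups. They do not favor leaving the reporting unit undefined in the SAP.

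**Conclusion.** The point holds conditionally. It is certain from the text that treatment group is undefined, that the SAP's stated columns are region and overall, that Cohorts B and C are broad enough to hold different drugs, and that mg/day is not tied to a drug. It is not established that any cohort actually holds more than one regimen.

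If one does, the understatement depends on the shares and on the rate under the other regimen: 20% shown as 8.8% to 16.3% if the other rate is 5%, and as 5% to 15% in the extreme case of 0%, at shares of 25% to 75%. The shares and the other regimen's rate are assumptions. Toxicity common to both regimens is not diluted. Pooling the exposure of drugs on such different mg scales would be uninterpretable at any material mix. The change is worth making because the drug taken is already on the CRF and it serves the sole objective.

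**What to change.** In Protocol 9.7.1.6 and SAP 4.2 and 6.5:

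1. Define treatment group as the regimen actually taken at roll-over entry, for example lenvatinib plus everolimus, lenvatinib plus pembrolizumab, sorafenib or sunitinib, limited to those that enrolled. The inclusion criteria require only that at least one parent-study drug is still being taken, so state that a subject who has already stopped one component is classed by the drug or drugs still taken.
2. Keep cohort subtotals alongside the region and overall columns.
3. Summarize exposure separately for each drug.
4. Show by regimen the TEAE overview and the tables of Grade 3 or higher events, serious events and events leading to discontinuation. Let the discontinuation table cover any study drug, since a lenvatinib-only table cannot count comparator subjects.
5. Use counts where a regimen has few subjects, and put the regimen on every adverse event listing.

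The cost is wording, table shells and programming; no new data are needed. The drawback is sparse columns with wide intervals. If each cohort turns out to hold one regimen, the change does little more than label those columns.
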